7.7 Early Withdrawal of Subjects

- Subjects should be withdrawn from the study if they no longer wish to participate, are being uncooperative, or if the investigator feels that it is in the best interest of the subject to withdraw.
- Subjects with protocol deviations or who were later discovered to not have met exclusion criteria should not be withdrawn unless there is a safety concern. The protocol deviation should be recorded in the subject’s chart and Protocol Deviation Form and included in the study report.
- Subjects who experience an AE resulting in or requiring discontinuation of study product use should be encouraged to be followed in the study until the AE is resolved or stabilized.

4. If a female subject becomes pregnant during the study, study product will be discontinued immediately and she will be followed through the pregnancy and delivery. Details of the pregnancy, delivery and health of the infant should be recorded on the Pregnancy Report Form and the sponsor notified immediately.
5. At the time of study discontinuation, the investigator will record the reason for early withdrawal, date of last dose application, date of last visit or contact, collect AE data, and, if possible, perform all Day 21 visit-specific evaluations. Every attempt should be made to contact subjects who are lost-to-follow-up for a final safety assessment. At least three attempts must be documented in the subject's chart including the use of at least 1 certified letter. Any contact, either direct or indirect, should be made with the purpose to document the final status of the subject with regard to safety.
6. Subjects who withdraw early will not be replaced.

7.8 Modification of Protocol

No amendments to this protocol can be made without consultation with and agreement of the Sponsor. Amendments must be made in writing and requires IRB approval. Modifications needed for the safety of subjects will be made immediately with notifications made as soon as possible.

7.9 Early Termination of Study

If it is determined by the sponsor or investigators that the study presents an unreasonable and significant risk to subjects, the study will be terminated as soon as possible, and in no event later than 5 working days following the determination that the study should be discontinued. The IRB and FDA must be notified as soon as possible about early termination of the study due to safety concerns.

7.10 Study Schedule

The study schedule chart is provided in [Table 1](#).

7.10.1 Screening Visit (Day -21 to Day -1)

1. Obtain written assent and/or informed consent prior to initiating any study procedures. Provide subject with signed copy of "Information and assent"/consent form. Document assent and/or informed consent in the subject's study record.
2. List subject on Screening/Enrollment Log and assign subject number. Subject numbers consist of the 3-digit site number followed by sequential 3-digit numbers usually starting with 001 (e.g., 206001, 206002, 206003). All subjects including screen failures will also be assigned a subject number.
3. Collect demographic data - date of birth, sex, race, and ethnicity.
4. Review and record medical history, acne history (including naïve vs previous therapy, acne treatment received 12 months prior to screening, onset date for acne and first acne treatment, previous use of Tazorac and any issue with Tazorac use), and concomitant medications, therapies, and procedures. Medical history and acne history should be collected for the prior 1-year period and concomitant medications, therapies, and procedures collected from the prior 6-month period. Only ongoing medical history items and ongoing concomitant

medications should be entered on the CRF. Acne history will be collected and recorded in the CRF. Review and record alcohol, drug and smoking history, to include history or presence of alcoholism (i.e. alcohol in excess of 14 glasses/unit per week, with 1 unit=150 ml of wine or 360 ml of beer or 45 ml of 45% alcohol) and history of drug abuse within 2 years prior to first dose.

5. Perform acne evaluation (IGA and lesion count). IGA scoring will be done prior to lesion count.
6. Perform urine drug screen, alcohol breath test.
7. Perform physical examination.
8. Collect sitting vital signs (blood pressure and pulse), height, and weight.
9. Perform 12-lead electrocardiogram (ECG).
10. Collect blood sample for safety laboratory evaluations (chemistry, hematology, and serology including serum pregnancy test and urinalysis).
11. Collect AEs.
12. Screen subject according to the study inclusion/exclusion criteria to determine tentative eligibility.
13. Initiate any protocol-required washout, if applicable.
14. Schedule Day 1 visit. Inform subject that he or she will come to the clinical site on Day 1 from at least 6 hours prior to the evening dose until after the evening dose application.
15. For every screen failure subject, record the subject number, date of visit, date of consent, reason for screen failure, and study status (screen failure) in the CRF.
16. Remind the subjects to abstain from alcohol for 72 hrs prior to first dosing and during study duration. Subjects who are smokers will be reminded to smoke no more than 10 cigarettes per day (or the equivalent for other nicotine containing products) during non-confinement days (except Day 13 and Day 20). They should also be instructed to abstain from smoking or using any products containing nicotine (including electronic cigarettes) 1 day prior to confinement days (Day 13 and Day 20) and during confinement.

7.10.2 Day 1

Subjects will be come to the clinical site prior to the first (evening) study dose application on Day 1, allowing sufficient time for all pre-dosing activities to be performed. Baseline assessments will be followed by evening dose application of Test or Reference treatment (as per randomization). Subjects will leave the clinic after the Day 1 evening dose application.

The procedures will be followed as per the study schedule.

1. Update the medical history and concomitant medications. Any medical event (not related to a protocol intervention) that occurred after the “Information and assent”/informed consent form was signed should be recorded as medical history. Only ongoing medical conditions and ongoing concomitant medications should be entered on the CRF.
2. Collect AEs. Any new medical event or need for medication caused by a protocol procedure

- performed at the Screening Visit should be considered an AE except for worsening of acne.
3. Assess severity of acne using IGA and measurement of lesion count. IGA scoring will be done prior to lesion count prior to first dose. IGA scoring will be done prior to lesion count.
 4. Perform a urine pregnancy test for female subjects of childbearing potential. Record method of contraception, as applicable, on source only.
 5. Perform urine drug screen and alcohol breath test. Any subject with a positive alcohol breath test and/or positive drug screen should not be randomized.
 6. Perform physical examination.
 7. Collect sitting vital signs (blood pressure and pulse), and weight prior to first dose.
 8. Perform 12-lead electrocardiogram (ECG) pre-dose.
 9. Collect blood sample for safety laboratory evaluations (chemistry, hematology, and urinalysis).
 10. Confirm eligibility according to inclusion/exclusion criteria.
 11. Randomize subject.
 12. Prior to first evening dose, visually inspect the skin and grade erythema, scaling/peeling.
 13. Collect pre-dose pK blood sample.
 14. Administer first dose.
 15. After administering first dose, collect sitting vital signs within 1 hour post-dose.
 16. Perform local cutaneous safety evaluation for dryness, non-lesional erythema, and peeling. The investigator or designated trained site staff should also ask the subject if any burning, stinging, or itching has occurred. These evaluations should be recorded separately for the face and, if applicable, neck, chest and/or back (including shoulders).
 17. Complete the CRF for randomized subjects.

7.10.3 Daily, Day 2 Through Day 20

Subjects will come to the clinical site ± 1 hour of each dose application (except Day 14). Subjects assigned to Test product will come to the clinical site for evening and morning twice-daily application and subjects assigned to Reference product will come to the clinical site for evening application. Subjects will leave clinic after completion of clinical activities for each dose application.

Subjects will be confined to the clinic from prior to evening dose application of Test or Reference on Day 14, allowing sufficient time for all pre-dosing assessments to be performed, until after the 24-hour PK sample collection and evening dose application on Day 15.

1. On Day 7 and Day 14, prior to evening dose application, perform urine pregnancy test for female subjects, urine drug screen and alcohol breath test. Any subject with a positive alcohol breath test and/or positive drug screen should be discontinued from the study.
2. Alcohol breath test will be additionally performed on Days 12, 13, 19 and 20. Any subject with a positive alcohol breath test and/or positive drug screen should be discontinued from

the study.

3. On Day 14, collect sitting vital signs (blood pressure and pulse) pre-evening dose and at 1, and 8 hours after evening dose application for Test and Reference product.
4. On non-confinement days (Days 2-13 and Days 15-20), collect sitting vital signs (blood pressure and pulse) pre-evening dose (within 15 minutes of dosing) and within 1 hour after evening dose application for Test and Reference.
5. On Days 12 and 13 (steady state), collect PK blood sample. Additionally trough samples will be collected at Day 19 and Day 20. For the pediatric population in Part B, trough samples will not be collected on days 12, 13, 19 and 20.
6. On Day 15, prior to the evening dose application for Test and Reference products, assess severity of acne by IGA scoring and measurement of lesion count. IGA scoring will be done prior to lesion count.
7. Prior to each dose application, visually inspect the skin and record erythema and scaling (peeling) grades.
8. Apply assigned study product (morning and evening applications for subjects assigned to the Test product, evening application for subjects assigned to Reference product).
9. After each dose application, perform local cutaneous safety evaluation for dryness, non-lesional erythema, and peeling within 1 hour of dosing. The investigator or designated trained site staff should also ask the subject if any burning, stinging, or itching has occurred on the face since the last application. These evaluations should be recorded separately for the face and, if applicable, chest/back (including shoulders).
10. Collect AE data.
11. Update concomitant medications data.
12. Subjects will leave the clinical site after completion of the clinical activities except as noted below for Days 14 to 15.
13. On Day 14 subjects will be housed at the clinical site from prior to the evening dose application, allowing sufficient time for all pre-dosing assessments to be performed, until after the 24-hour PK sample has been collected on Day 15. The morning dose application for Test treatment will be performed on the morning of Day 15. The 24-hour PK sample collection will be followed by the Day 15 evening dose application for Test and Reference product.
14. On Days 14 to 15, PK blood sample collection will occur at the following times:
In Part A (adult subjects, age 17 years or older), blood samples will be collected prior (pre-dose) to the Day 14 evening dose application for Test and Reference treatments and at 1, 2, 4, 6, 8, 12, 14, 16, 18, and 24 hours post dose application.
15. In Part B for Test treatment (subjects age 9 years to 16 years 11 months) and Reference treatment (subjects 12 years to 16 years 11 months), a maximum of 4 blood samples will be collected as per the sparse sample design ([Table 3](#)) Complete the CRF.

7.10.4 Days 21 and 22

Subjects will be confined to clinic prior to evening dose application of Test or Reference treatment, allowing sufficient time for all pre-dosing assessments to be performed on Day 21 until [the completion of clinical activities per schedule](#) on Day 22.

1. On Day 21, perform physical examination.
2. On Day 21, update concomitant medications.
3. On Day 21 prior to evening dose application in evening for Test and Reference treatments, perform urine pregnancy test for female subjects, urine drug screen and alcohol breath test. Any subject with a positive alcohol breath test and/or positive drug screen should be discontinued.
4. On Day 21, perform 12-lead ECG pre-dose.
5. Prior to dosing on evening of Day 21 for Reference treatment and morning treatment of Day 22 for Test treatment, assess severity of acne by IGA scoring and measurement of lesion count. IGA scoring will be done prior to lesion count.
6. Prior to each dose application, visually inspect the skin and record erythema and scaling grades.
7. Apply assigned study product for the Day 21 evening dose application for Test and Reference treatments. For subjects assigned to Test treatment, the morning dose application will be performed the morning of Day 22 and this last dose application will not be rinsed off in the shower.
8. After each dose application, perform local cutaneous safety evaluation for dryness, non-lesional erythema, and peeling within 1 hour of dosing. The investigator or designated trained site staff should also ask the subject if any burning, stinging, or itching has occurred on the face since the last application. These evaluations should be recorded separately for the face and, if applicable, chest/back (including shoulders).
9. On Day 21, collect sitting vital signs (blood pressure and pulse) pre-evening dose and at 1 and 8 hours after evening dose application for Test and Reference treatments. (Note that the 8-hour post dose vital sign will occur on the morning of Day 22).
10. On Days 21 to 22, PK blood sample collection will occur at the following times:

In Part A (adults, age 17 years or older), blood samples will be collected prior (pre-dose) to the Day 21 evening dose application for Test and Reference treatments and at 1, 2, 4, 6, 8, 12, 14, 16, 18, and 24 hours post dose application.

In Part B for Test treatment (subjects age 9 years to 16 years 11 months) and Reference treatment (subjects 12 years to 16 years 11 months), a maximum of 4 blood samples will be collected as per the sparse sample design ([Table 3](#)).
11. On Day 21, collect blood sample for safety laboratory evaluations (chemistry, hematology, and urinalysis).
12. Collect AE data.
13. Complete CRF.

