7. Sitting blood pressure, pulse rate at pre-dose and at 1 and 8 hours after evening dose application with an allowable window of \pm 15 minutes on Day 14 and Day 21. On non-confinement days, sitting vital sign measurements will be done pre-evening dose (within 15 minutes of dosing) and within 1 hour after evening dose application.
8. Blood sampling for pharmacokinetics will be done at pre-specified time points (for Part A) and sparse sampling for Part B, as described in [Table 2](#) and [Table 3](#), respectively. Allowable sampling window is \pm 15 minutes for each timepoint.
9. Disease severity assessment will be performed by Investigator's Global Assessment (IGA) score and lesion counts at baseline and at PK Sampling days.
10. Before each dose application, the investigator or designated trained site staff will visually inspect the skin and grade erythema and scaling/peeling. After each dose application (within 1 hour of dosing), the investigator or designated trained site staff will assess application site reactions of non-lesional erythema, peeling, dryness and ask the subject if any stinging, burning, or itching has occurred.

11. Adverse events will be collected from signing of the Informed Consent at Screening through end of the study and any adverse events spontaneously reported by subjects for a period of 30 days following the last blood sample of the study.

Table 2: Schedule of Blood Sample Collection for Pharmacokinetic Analysis

Day	Part A (Adults: 17 years or older)		Part B (Pediatrics)	
	Test Treatment	Reference Treatment	Test Treatment (9 years to 16 years 11 months)	Reference Treatment (12 years to 16 years 11 months)
1	Prior to evening dose	Prior to evening dose	Prior to evening dose	Prior to evening dose
12	Prior to evening dose	Prior to evening dose		
13	Prior to evening dose	Prior to evening dose		
14-15	Prior to evening dose and serial sampling at 1, 2, 4, 6, 8, 12, 14, 16, 18, and 24 hours post 1st evening dose application.	Prior to evening dose and serial samples at 1, 2, 4, 6, 8, 12, 14, 16, 18 and 24 hours post dose application.	Sparse ¹ samples) as per sampling design in Table 3	Sparse ¹ samples as per sampling design in Table 3 .
19	Prior to evening dose	Prior to evening dose		
20	Prior to evening dose	Prior to evening dose		

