7.6 Safety Assessments

Safety assessments include visual inspection of the skin (erythema, scaling [peeling]) prior to dose application, assessment of application site reactions (dryness, non-lesional erythema, peeling, stinging, burning, and itching) after dose application, clinical safety laboratory evaluations (chemistry, hematology, and urinalysis), and physical examinations including vital signs (blood pressure and pulse rate). A 12-lead ECG will be performed at the Screening Visit, Baseline visit (Day 1) and Day 21. For females of childbearing potential serum pregnancy tests will be conducted at the Screening Visit and urine pregnancy tests will be conducted at Day 1, Day 7, Day 14 and Day 21. Adverse events will be collected by spontaneous reports from subjects, by directed questioning of subjects, and by observation (see Section 8 for details about AEs). Adverse events, whether believed by the investigator to be related or unrelated to treatment, will be recorded on the CRF.

Before each dose application, the investigator or designated trained site staff will visually inspect the skin and grade erythema and scaling using the scales shown in [Table 6](#) and [Table 7](#), respectively.

After each dose application, the investigator or designated trained site staff will assess application site reactions by examining treated areas for clinically significant non-lesional erythema, peeling, and dryness that will be graded as shown below ([Table 6](#), [Table 7](#), [Table 8](#)) and recorded on the CRF. Assessments will be recorded separately for the face and (if applicable) neck, chest and/or back (including shoulders). The investigator or designated trained site staff will also ask the subject if any stinging ([Table 9](#)), burning ([Table 10](#)), or itching ([Table 11](#)) has occurred on the face (neck, chest and/or back (including shoulders), if applicable since the previous drug application. Day 1 assessments are made prior to first application. An AE should be recorded if the severity is worse than at Day 1. In addition, overall cutaneous tolerance should be graded at Day 21, or the last visit if earlier, using the grading shown in [Table 12](#). The local cutaneous tolerance signs and symptoms will be assessed separately for the

face and neck, chest and/or back (including shoulders) using the same scales below and should be performed within 1 hour of dose application.

Table 6: Scoring of Non-Lesional Erythema

Severity	Score	Description

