8 ADVERSE EVENTS

Adverse events will be collected by spontaneous reports from subjects, either verbal or recorded in the subject diary, by directed questioning of subjects, and by observation.

The most common frequently reported adverse reactions during clinical trials with tazarotene cream 0.1% for the treatment of acne were desquamation, dry skin, erythema, and burning sensation, occurring in 10% to 30% of subjects. Adverse reactions occurring in 1% to 5% of treated subjects included pruritus, irritation, face pain, and stinging.

The investigator is to pay special attention at each visit to any signs of clinically significant dryness, non-lesional erythema, and peeling and report as an AE subsequent to the Baseline Visit if worse than at Baseline.

An AE is any untoward medical occurrence in a subject participating in a clinical trial. The event does not necessarily have to have a causal relationship with the study product. An AE can therefore be any sign, symptom, or disease, or any worsening of an existing sign, symptom, or disease, whether or not considered related to the study product or trial procedures, including injuries.

Any medical condition that is present at the time of Screening or Baseline should be considered as medical history and reported on the medical history CRF and should not be reported as an AE except for AEs observed at the Baseline Visit due to study procedures performed at the Screening visit, which should be reported. Anticipated day-to-day fluctuations of pre-existing conditions should not be reported as AEs. Unexpected worsening of pre-existing conditions should be reported as AEs. The disease or condition being studied or expected progression, signs, or symptoms of the disease or condition being studied such as worsening of acne should not be reported as an AE unless it is more severe than expected, results in discontinuation from the study or requires alternative therapy.

All serious adverse events (SAEs), all study product-related events, and all AEs leading to study product discontinuation must be followed until the clinical outcome is determined or until all attempts to determine resolution of the event are exhausted (not recovered is not an acceptable outcome for acute conditions). For other AEs, the status at the last visit can be entered into the CRF.

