11.5.2 Local Cutaneous Safety Evaluation

Non-lesional erythema, peeling, dryness, burning, stinging, and itching scores will be summarized by treatment group and visit including sample size, frequency count and percentage for each visit. A similar summary will be provided excluding subjects with signs or symptoms present at Baseline.

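### Four of the six local tolerability items have no scheduled score before the first dose, although Section 7.6 makes Day 1 a pre-dose reference for recording adverse events

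*Combined protocol and SAP*

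**What the plan says.** Six local reactions are graded: non-lesional erythema, peeling/scaling, dryness, stinging, burning and itching (Section 7.6, Tables 6 to 11).

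- **Section 7.6**, after describing the grading of all six: "Day 1 assessments are made prior to first application. An AE should be recorded if the severity is worse than at Day 1".
- **Section 7.10.2, opening paragraph:** baseline assessments come first and the evening application follows them.
- **Section 7.10.2, item 12 (before the dose):** "Prior to first evening dose, visually inspect the skin and grade erythema, scaling/peeling". Item 14 is the first dose.
- **Section 7.10.2, item 16 (after the dose):** "Perform local cutaneous safety evaluation for dryness, non-lesional erythema, and peeling", followed by "The investigator or designated trained site staff should also ask the subject if any burning, stinging, or itching has occurred".
- **Table 1, footnote 10:** only erythema and scaling/peeling are graded before each dose. After each dose, within 1 hour, staff "will assess application site reactions of non-lesional erythema, peeling, dryness and ask the subject if any stinging, burning, or itching has occurred".
- **Section 8** has a second trigger, for dryness, non-lesional erythema and peeling: "report as an AE subsequent to the Baseline Visit if worse than at Baseline".
- **Section 11.5.2** tabulates all six scores by treatment group and visit, then adds: "A similar summary will be provided excluding subjects with signs or symptoms present at Baseline". It does not define Baseline.

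**The concern.** Safety and tolerability is a secondary objective (Section 3). Two parts of its assessment need a Day 1 reference: the rule for when a graded reaction becomes an AE, and the second Section 11.5.2 table, which is meant to isolate irritation that was not there at the start.

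For dryness, stinging, burning and itching, the step list that staff work from produces only one Day 1 score, and it is taken after product has been applied. If that score is used as the reference, a reaction to the first application is compared with itself. If it is not used, there is nothing to compare with. Either way, existing dryness or itching cannot be told apart from a first-dose reaction. Such existing symptoms are plausible, because topical retinoids and benzoyl peroxide need only a 14-day washout before Baseline (Section 5.3, Table 4).

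**Working it through.** No sample size, power or event figure is involved. The check sets the texts side by side and then follows their consequences.

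**1. When is each item scored on Day 1?**

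| Item | Section 7.6 Day 1 rule | Section 7.10.2 items 12-16 | Table 1 footnote 10 |
|---|---|---|---|
| Non-lesional erythema | pre-dose | pre and post | pre and post |
| Peeling/scaling | pre-dose | pre and post | pre and post |
| Dryness | pre-dose | post only | post only |
| Stinging | pre-dose | post only | post only |
| Burning | pre-dose | post only | post only |
| Itching | pre-dose | post only | post only |

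Items with no scheduled pre-dose step: 6 − 2 = 4.

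**2. Could a screening score stand in?** No. The Table 1 row for local cutaneous reactions starts at Day 1, and the screening list in Section 7.10.1 contains no tolerability grading.

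**3. What does the choice of reference do?** Take three hypothetical subjects scored on one of the four items, using the protocol's 0 to 3 grades.

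| Subject | Before dose 1 | After dose 1 | Later visits | Reference = pre-dose | Reference = post-dose |
|---|---|---|---|---|---|
| A: reacts at dose 1, stays the same | 0 | 2 | 2 | AE rule met (2 > 0); kept in second table | AE rule not met (2 = 2); left out of second table |
| B: symptom already present | 1 | 1 | 1 | AE rule not met; left out of second table | same |
| C: reacts later | 0 | 0 | 2 | AE rule met; kept in second table | same |

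Only subject A is classified differently. Without a pre-dose score, A (post-dose 2) and a subject who arrived with grade 2 look identical.

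**4. Can the size be estimated?** Section 8 reports dry skin and burning in 10% to 30% of subjects on tazarotene cream 0.1%, and pruritus and stinging in 1% to 5%. If *f* is the share of reactors who behave like subject A, the incidence recorded through this rule is the true incidence × (1 − *f*). The documents give no information on *f*, on when reactions start, or on which score sites would use. The formula therefore yields no usable figure.

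**The case against.** **The plan does not adopt a post-dose baseline.** A reader might infer from the step list that first-dose irritation becomes the baseline. The documents do not support that: Section 7.6 and the opening of Section 7.10.2 both put the Day 1 assessment before dosing. This stands. The defect is an inconsistency, and masking follows only if a site works from the numbered list and takes its one Day 1 score as the reference. The general statements do not cure it, though, because no listed step carries them out for the four items.

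**Nothing need be hidden.** A reader might also infer that such reactions vanish from the report. They would not. The main Section 11.5.2 table would show the Day 1 post-dose scores. The Section 8 definition of an AE covers any sign or symptom, AEs are also collected by spontaneous report, questioning and observation, and overall tolerance (Table 12) is graded without reference to baseline. This stands too, with two limits. The treatment-emergent rule in Section 11.5.3 counts only events already recorded as AEs. The by-visit table cannot separate new symptoms from existing ones.

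**Unequal masking between arms is not shown.** The cream stays on for 12 hours and the lotion for about 1 minute (Section 6.2), so one might expect a post-dose reference to affect the arms differently. The documents give no timing of reactions, and later visits ask about symptoms since the previous application. This remains conjecture.

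**Conclusion.** The concern holds as an internal contradiction with a conditional consequence. Section 7.6 requires a pre-dose Day 1 reference, while Section 7.10.2 items 12 to 16 and Table 1 footnote 10 schedule none for dryness, stinging, burning and itching. If the post-dose score is used instead, first-dose irritation that does not worsen may fail to trigger the AE rule, and those subjects may drop out of the additional baseline-excluded table. Erythema and peeling are unaffected.

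The size cannot be estimated from the documents. The affected output is a descriptive secondary analysis in which other routes could still show the reaction. The point is nevertheless worth correcting: a pre-dose score that was not taken cannot be recovered later, and taking it is cheap.

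**What to change.** 1. In Section 7.10.2 and Table 1 footnote 10, list a Day 1 score for all six items before the first application, so that both agree with Section 7.6.
2. Define Baseline as that pre-dose score for the AE triggers in Sections 7.6 and 8 and for both summaries in Section 11.5.2.
3. Keep the post-dose Day 1 score and label it the first on-treatment assessment.
4. Part A has already been run (Section 7.5), and the documents do not show how its sites scored these items. For any Part A subject with only a post-dose Day 1 score on the four items, treat the baseline as missing and flag it. Using the post-dose score as baseline would absorb first-dose reactions. Counting every post-dose sign as a product reaction would make the opposite error for subjects like B above.

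The separate statistical analysis plan is due before database lock (Section 11), so items 2 to 4 can be written there. The cost is a few extra minutes at the Day 1 visit and one CRF line.

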6.5 Blinding

Study treatment will be open-label during the study conduct. However, the plasma samples provided to the designated laboratory for determination of tazarotene and tazarotenic acid will be coded to ensure that the identity of the treatments is not known when the plasma samples are analyzed.

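### The only pre-dose Day 1 skin grades are listed after randomisation in an open-label trial, which exposes the tolerability baseline to avoidable detection bias

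*Combined protocol and SAP*

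**What the plan says.** **Order of steps on Day 1 (7.10.2).** IGA and lesion counts are item 3, the physical examination is item 6 and confirmation of eligibility is item 10. Item 11 is "Randomize subject". Item 12 is "Prior to first evening dose, visually inspect the skin and grade erythema, scaling/peeling". The PK sample follows at item 13 and the first dose at item 14. Item 16, after that dose, is "Perform local cutaneous safety evaluation for dryness, non-lesional erythema, and peeling", together with questions about burning, stinging and itching.

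**Masking and graders.** Section 6.5 states: "Study treatment will be open-label during the study conduct". Only the plasma samples sent to the laboratory are coded. Section 7.6 assigns the grading to the site: "Before each dose application, the investigator or designated trained site staff will visually inspect the skin and grade erythema and scaling".

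**Use of the baseline grade.** Section 7.6 says: "Day 1 assessments are made prior to first application. An AE should be recorded if the severity is worse than at Day 1". Section 8 repeats the rule with Baseline as the comparator, for clinically significant dryness, non-lesional erythema and peeling. Section 11.5.2 summarises the scores by group and visit and then adds: "A similar summary will be provided excluding subjects with signs or symptoms present at Baseline".

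**The concern.** Tolerability is a stated secondary objective, and in this plan the baseline skin grade does two jobs. It sets the level above which a later grade becomes an adverse event, and it helps define a subset for analysis. If the grader knows the arm, expectation about either product can move that grade. A higher baseline in one arm leaves fewer later grades counting as worse and removes more of its subjects from the 11.5.2 subset. A lower baseline does the reverse.

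The expectation is not far-fetched. Section 8 lists the irritation known from tazarotene cream 0.1%, with several reactions in 10% to 30% of subjects. Section 6.2 has Test rinsed off after about a minute and Reference left on for 12 hours. The step from score 0 to score 1 in Tables 6 and 7 is fine enough for judgement to matter.

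Unmasked grading after baseline is a consequence of the open-label design. Unmasked grading at baseline is largely avoidable.

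**Working it through.** The plan states no figure on this point, so the check is of sequence and use, followed by arithmetic for scale.

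**1. Is there an earlier graded score?** The Screening list (7.10.1) has none, and the local-reaction row of Table 1 is empty at Screening. The item 6 physical examination reviews the skin (11.5.6) but does not use the Table 6 and 7 scales. Item 12 is therefore the first graded score.

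**2. Does any other text place the grading before randomisation?** Section 7.6, Table 1 footnote 10 and the opening paragraph of 7.10.2 all time it against dosing. None times it against randomisation, so nothing overrides the order of items 11 and 12.

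**3. Which signs have a pre-dose Day 1 grade?**

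| Sign | First Day 1 grade in 7.10.2 | Relative to randomisation | Relative to first dose |
|---|---|---|---|
| Erythema | item 12 | after | before |
| Peeling/scaling | item 12 | after | before |
| Dryness | item 16 | after | after |
| Stinging, burning, itching | item 16 | after | after |

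The last two rows conflict with the statement in 7.6 that Day 1 assessments precede the first application. As 7.10.2 stands, four of the six signs have no pre-dose baseline.

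**4. Scale.** Section 4 plans 12 Test and 12 Reference subjects in Part A, and up to about 26 Test and 12 Reference in Part B. One subject is worth:

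- Part B Reference: 1/12 = 8.3 points
- Part B Test: 1/26 = 3.8 points
- Reference overall: 1/(12 + 12) = 1/24 = 4.2 points
- Test overall: 1/(12 + 26) = 1/38 = 2.6 points

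These are the exact effects of one changed 0/1 grade on the percentage of an arm with that sign at baseline. For the percentage with an adverse event they are maxima: the count moves only if the later grade falls where the changed baseline alters the answer. The documents do not say how often a grade would be altered.

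**5. Who could benefit from reordering?** Inclusion criterion 3 admits subjects under 12 to Test only, and section 4 requires at least 6 aged 9 to 11. Their arm is known from age before any randomisation step. At most 38 − 6 = 32 Part B subjects could be graded without knowledge of the arm, of whom at most 26 − 6 = 20 are on Test.

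**The case against.** The strongest reply is that the sequence and the grader's knowledge are both inferred. Section 7.10.2 refers to the study schedule, and Table 1 gives no order within a day. The companion list in 7.10.4 is not in time order: dosing is item 7, while the pre-dose vital signs and PK sample are items 9 and 10. No sentence says when the assignment becomes known to the person grading. This stands as a limit on certainty. But items 10 to 14 of Day 1 do read as a sequence, and nothing in the plan keeps the assignment from the grader.

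The second reply is that little depends on it. The local scores are summarised descriptively with no planned between-arm test, and the primary endpoints come from coded samples. Later grading is unmasked and also unequal, since it accompanies 42 Test applications against 21 Reference. This stands too: it lowers the priority, and reordering would not cure it.

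Two stronger readings are tempting. A reader might call this allocation bias. By item 12 the assignment is already made and the grade cannot affect it, so the risk is detection bias in a baseline measurement. A reader might also assume different baseline rates in the two arms and derive a definite shift in adverse event rates. No rate in the documents supports that. Section 8 asks for clinically significant signs, whereas 7.6 also has the bare rule "An AE should be recorded if the severity is worse than at Day 1", so how many one-step changes become events is uncertain. Nor does item 12 alone determine the 11.5.2 subset, because that exclusion covers any sign or symptom at Baseline.

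**Conclusion.** The point holds as a modest, avoidable weakness. The first graded erythema and scaling/peeling scores are listed after randomisation with no masking of the grader. They then serve as an adverse event comparator and contribute to selecting the 11.5.2 subset. For dryness, stinging, burning and itching, 7.10.2 gives no pre-dose grade at all, and it must be reconciled with 7.6.

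The conclusion assumes that the Day 1 list is followed in order and that site staff learn the arm at item 11. The size and direction of any bias cannot be estimated; in the smaller Part B arm a single altered grade can matter by up to 8.3 points. The documents do not show that differential grading occurred, and the primary PK comparison is not touched. Priority is low to moderate.

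**What to change.** Section 7.5 reports that the Part A PK assessment is already done, so the change is for Part B.

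- In 7.10.2, place the Day 1 baseline grading of all six signs and symptoms between item 10 (confirm eligibility) and item 11 (randomise), with the grades recorded before the assignment is opened.
- Keep the item 16 evaluation and label it post-baseline. This also removes the conflict with 7.6.
- In the pre-dose part of Table 1 footnote 10, add the words *on Day 1, before randomization*, and make the list of signs there match.

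The cost is a reordering of the list, one footnote and one recording rule. Four signs now first assessed after the dose would also be recorded before it, at a visit where the skin is already being graded. No visit or staff is added. The text should acknowledge that masking at baseline is not achievable for subjects aged 9 to 11 and that all post-baseline grades remain unmasked.
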